# 4.5.3 Confidentiality procedures

All DSRU staff sign confidentiality agreements and the DSRU is registered with the office of the Data Protection Registrar (Registration No. Z5438861).

DSRU information security policies are in place to preserve the confidentiality, integrity and availability of the organisation's systems and data. These include ensuring the premises provides suitable physical and environmental security, all DSRU equipment is secure and protected against malicious software, the network can only be accessed by authorised DSRU staff, telecommunication lines to the DSRU premises are protected from interception by being routed overhead or underground and personal receive training regarding security awareness.

All original documents, individual correspondence from specialist HCPs, will be stored for 15 years at the DSRU, with considerable care taken to preserve the confidentiality of data. The DSRU databases are well protected. To ensure patient anonymity, the names and addresses of patients will be deleted from the DSRU database at an appropriate time point (provisionally this is at datalock or earlier if patients have provided informed notification that they wish to withdraw from the study, but the DSRU will request an extension to this to comply with CHMP requirements). Until this time, only appointed staff would have access to such data.

# 4.6 Quality Assurance

Good clinical data management is a high priority at the DSRU. A number of strategies exist to minimise biased event monitoring study results. The DSRU has a set of rules and processes associated with the conduct of pharmacoepidemiological studies. Data quality is assured through a number of methods based on error-prevention, data monitoring, data cleaning and documentation. These include:

- Operator training;
- Vigilance of operators at the various stages of processing,
- On screen validation during data entry,
- Adoption of and adherence to study-specific data coding conventions,
- Coding review meetings,
- Code list and algorithms
- Double entry (100% of questionnaires), error reporting and correction of discrepancies between the entries by quality assurance staff
- Coding of questionnaires are randomly reviewed by a quality assurance assessor.
- Routine data cleaning to screen for errors, missing values and extreme values and diagnose their cause; this being supported by bespoke software with objective, standardised logical checks and undertaken by the DSRU data manager or allocated staff.
- Relevant maintenance of reference tables, e.g., Event Dictionary
- Pilot testing of study documentation

## 4.7 Data analysis

# 4.7.1 Cohort accrual, the type of specialist HCP responsible for, the setting of initiation of treatment, specialist HCP preference factors and non-clinical reasons for prescribing

The following relates to Section 2.2.2 Secondary objectives (i) and (ii). Data on specialist HCP response rates will be presented, as will data on prescriber demography, type, setting and institution, specialist HCP preference factors and non-clinical reasons for prescribing. These data will be used to inform on cohort accrual and study timelines to target sample size.

Cohort accrual will be summarised with description of losses to follow-up and withdrawals. [39] Patients who decline to participate will be compared to those who provide consent (through use of data collected on the invitation log) in terms of demographic variables to assess potential for selection bias through non-participation. Similarly, patients who are lost to the study because of withdrawal of consent, or because of attrition will be compared to those who remain in the study to examine whether there are any systematic differences in demographic or treatment variables which may affect internal validity or generalisability.

# 4.7.2 To estimate the cumulative incidence of the important identified risk of haemorrhage for rivaroxaban.

The following relates to Section 2.2.1 primary objective (i) for rivaroxaban only and relates to haemorrhage within gastrointestinal and urogenital organ sites (which meets the criteria for a major bleed) and all intracranial sites (as defined in Table 2)..

For the three organ sites specified in the primary outcome, each of the individual components of the major bleeding criteria (a fall in haemoglobin of 2 g/dL or more, or a transfusion of 2 or more units of packed red blood cells or whole blood, or a fatal outcome - as per table 2) will be summarised. Where an individual has one or more criterion for an individual organ site of interest, this will also be summarised – in such individuals the first report will be regarded as the incident event. The cumulative incidence (risk) of the primary outcomes reported during treatment within the 12 week observation period will be explored by estimating the cumulative incidence of incident reports (plus 95% CI) and cumulative hazard rates (plus 95%CI) of incident events over time. For purposes of this analysis the denominator (personperiod at risk) is defined as the 12 week observation period (i.e., the time from the date the first prescription was issued for rivaroxaban (treatment index date) until the date of stopping (+ 2 days) or at 12 weeks if patient did not stop, whichever occurs first). The numerator will comprise of reports of incident major bleeding events during that 12 week observation period. These which have been adjudicated by expert review (using all available information from SCEM questionnaires, follow-up and any additional documentation). Where such information reveals that the event was misreported, that patient will excluded as a case from the analysis, but contribute person-time exposed.

The cumulative incidence will be calculated according to the formula:

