Period of observation for analyses will commence from index date (i.e. actual start date of anticoagulant treatment, not the date first seen by the specialist) and continue for 12 weeks (or less if patient discontinues to be under the care of the specialist HCP; to be established via the 12 week end of observation questionnaire) in order to allow for detection of outcomes associated with oral anticoagulant treatment initiation as recorded in medical charts. This study will also collect information on exposure to any other medicines (including those given as part of acute care management within the four calendar weeks prior to index date) as recorded in medical charts in order to explore impact of those treatments on outcomes of interest. Since patient care is likely to be shared between secondary and primary care for most patients during the 12 week observation period, the patient's GP will be contacted††† to complete a simple questionnaire to collect any information on outcomes of interest that have been recorded in the patient's medical charts held in primary care during the 12 week observation period to minimise under-reporting on selected outcomes. Where additional outcomes are identified that have not be reported by the initiating prescriber, these will be followed-up with the GP to ascertain further information.

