# 4.3.2.3 Evaluable patients.

Evaluable patients are those patients who have provided consent and for whom analysable clinical data has been provided in the data collection questionnaires. Evaluable patients for whom the second phase (12 week) survey questionnaire (from BOTH specialist HCP and GP) is returned blank (contain no clinical information) or has not been returned will only be included for analysis of secondary objectives (i) and, (ii).

Consented patients will not be considered evaluable if the specialist HCP reports that the patient did not take rivaroxaban or alternative anticoagulant therapy. If there is evidence to suggest duplication of patients, either through inadvertent duplication between different specialist HCPs within the same clinical setting, or if a patient was switched from rivaroxaban to alternative anticoagulant therapy, or there is a significant delay (>1 month) in receipt of phase 1 survey form then the patients identified will be considered for inclusion on a case by case basis by the study manager and/or project advisory committee.

<sup>1111 Any cases in which there is ambiguity relating to the indication for treatment will be reviewed on a case by case basis, in order to confirm the prescribing indication/indications.

<sup>§§§§ However, a patient under the age of 18 will be included in the study if, in what is expected to be rare situations, a doctor decides on the basis of his/her clinical judgement to prescribe rivaroxaban for such person. \*\*\*\*\*\* patients will be excluded if they are being treated with antiplatelet therapy exclusively

Patients will be automatically withdrawn if the patient or specialist HCP provides informed written or verbal notification that they no longer wish to participate at any stage of the study.

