# Total number of new cases during 12 week observation period x 100 Population initially at risk

If the observed cumulative incidence from the SCEM study falls within the range expected as set by the precision limits of cumulative incidence from clinical trial data, then the null hypothesis (of no difference) will not be rejected. Cumulative hazard rate methods account for truncation of exposure time and censoring; for these analyses the exposure time would be censored at the time of the first event. Kaplan-Meier plots will be presented to describe timeto event as well as smoothed hazard plots to describe how the baseline risk of an event changes over time. Estimates of the hazard function will also be modelled to determine whether the baseline hazard (risk) of the event increases or decreases with time. A constant hazard over time may be consistent with a background (not caused by the drug) event rate, whereas a non-constant hazard over time may be an indicator of a drug-event relationship. The null hypothesis that the hazard rate of the selected event in patients prescribed rivaroxaban will be constant during the 12 week period following the start of treatment will be tested by fitting a parametric time to event model (e.g. Weibull). Such models have a shape parameter that indicates whether the hazard is significantly increasing or decreasing over time. At least five reports of an event are deemed necessary for modelling purposes.\*\*\*\*\*\*

Several sensitivity analyses will be performed: In one, observation start date will be imputed to be the same as the diagnosis date (i.e the index date will be shifted backwards in time) for those patients for whom a lag period between diagnosis and receiving rivaroxaban treatment was reported. The application of time-varying covariates methodology will enable examination of the impact of any transition from other treatments given as part of initial standard care on the results. In addition, since the primary analysis will be run only to include confirmed cases of incident major bleeding, it will be necessary to explore the reasons for exclusion of incomplete cases and examine their impact on the estimated measure of frequency.

Where possible, data will be stratified according to relevant strong risk factors (e.g. gender, age ( $\leq 60, 60-74, \geq 75$  years), indication and past history of haemorrhage or VTE) and stratum-specific incidence rates examined.

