<sup>§§§§§§§ Ideally, the exposure time would be censored at the time of the first event. However, since there are a large number of health outcomes of interest and the censoring would be different for each outcome, the denominator for the crude ID will not initially include censoring. If an elevated crude ID is identified in this monitoring analysis, a subsequent analysis with appropriately censored denominator will be performed for that outcome.

Sensitivity analyses will examine any under-reporting by including events of interest recorded in primary care medical charts and confirmed on follow-up for those patients discharged to primary care, during the 12 week observation period.

As IDs for the overall cohort may sometimes mask significant signals in specific risk groups, the subgroups defined by specific characteristics (e.g. previous history of VTE or haemorrhage, previous/concurrent use of selected medications, off-label indication groups, rivaroxaban naïve or past user) will have IDs calculated and compared according to strata for relevant events, where appropriate.

It is possible to explore the time taken for an event of interest using parametric time to event models (e.g. Weibull) as described previously, thus providing an additional tool for signal generation purposes. This approach will be explored for events of interest, where counts  $\geq 5$ . If undertaken, a sensitivity analysis will be performed to include in the numerator events reported within 7 days of stopping, and extend the denominator by 7 days

4.7.6 To characterise differences in prevalence of prognostic factors and clinical risk factors for haemorrhage associated with rivaroxaban in comparison with contextual cohort as reported during the first 12 weeks after starting treatment in routine secondary care hospital setting in UK.

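### Section 4.7.2 counts time after discharge to the GP as event-free to week 12 even when no GP form is returned; this contradicts 4.1 and biases the bleeding incidence low

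*Supplement*

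**What the plan says.** - **Time at risk (4.7.2).** It runs from the first rivaroxaban prescription "until the date of stopping (+ 2 days) or at 12 weeks if patient did not stop, whichever occurs first". The only further censoring named, for the hazard analyses, is at the first event.
- **Cumulative incidence (4.7.2).** New cases in the 12 weeks are divided by the "Population initially at risk". The result is then held against limits taken from clinical trial data. Cases are adjudicated "using all available information from SCEM questionnaires, follow-up and any additional documentation".
- **Observation period (4.1).** It lasts 12 weeks, "or less if patient discontinues to be under the care of the specialist HCP". The same section explains why GPs are contacted: "Since patient care is likely to be shared between secondary and primary care for most patients during the 12 week observation period".
- **Evaluability (4.3.2.3).** A patient is restricted to secondary objectives (i) and (ii) only when the 12-week form "from BOTH specialist HCP and GP) is returned blank (contain no clinical information) or has not been returned".
- **GP form (4.4.2.4).** It covers the period from discharge to week 12, asks for events and for the date of stopping, and is described as an abridged SCEM questionnaire. Section 4.4.3.1 expects some specialists and GPs not to reply.
- **Event rates (4.7.5).** Incidence densities use on-treatment patient-weeks. On primary-care records the text says: "Sensitivity analyses will examine any under-reporting by including events of interest recorded in primary care medical charts and confirmed on follow-up". Section 4.7.4 also treats GP data as a sensitivity analysis.

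**The concern.** The protocol has two rules for when observation ends, and nothing reconciles them. Under the 4.7.2 rule, the period that only the GP form was meant to cover stays in the denominator when that form is absent. Events in that period can then reach the numerator only through hospital records. The GP form also asks for the stop date, so without it a patient who stopped in primary care may be treated as never having stopped.

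Missed events can only lower the incidence. In a safety study that compares its result with trial figures, the error runs towards false reassurance. None of the sensitivity analyses listed in 4.7.2 examines it.

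**Working it through.** **1. One patient under each rule.** Take a hypothetical patient discharged at the end of week 2, with no recorded stop, a completed specialist form and no GP form. Section 4.3.2.3 keeps the patient in, because one of the two forms is present. Section 4.7.2 gives 12 weeks at risk; section 4.1 gives 2. For the 10 weeks between, no primary-care data exist. The denominator of the simple proportion is one patient under either rule, so applying 4.1 alone would not repair that figure. It would only discard later events.

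**2. The plan's own figures (4.2.1), n = 3.84 × p(1 − p) / precision².**
- DVT/PE: 3.84 × 0.004 × 0.996 / 0.0039² = 1005.8 (stated 1005).
- AF: 3.84 × 0.007 × 0.993 / 0.0069² = 560.6 (stated 561).

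Both reproduce. Neither allows for unobserved time.

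**3. Size in 4.7.2.** The protocol gives no discharge share, discharge time or GP response rate, so all three are assumed: d = share discharged, 50–90%; w = mean discharge week, 2–6; r = GP response, 40–80%. Also assumed are a constant hazard, no early stopping, and no capture of post-discharge bleeds by the specialist form. The understated fraction is then U = d × (1 − r) × (12 − w)/12.

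| d | r | w | U | 0.40% (DVT/PE) reads | 0.70% (AF) reads |
|---|---|---|---|---|---|
| 0.5 | 0.8 | 6 | 0.5 × 0.2 × 6/12 = 5% | 0.38% | 0.67% |
| 0.7 | 0.6 | 4 | 0.7 × 0.4 × 8/12 = 19% | 0.33% | 0.57% |
| 0.9 | 0.4 | 2 | 0.9 × 0.6 × 10/12 = 45% | 0.22% | 0.39% |

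**4. Effect on the comparison with trial data.** The upper limits are 0.40 + 0.39 = 0.79% for DVT/PE and 0.70 + 0.69 = 1.39% for AF. Exceeding them takes at least 8 cases in each group (0.0079 × 1005 = 7.9; 0.0139 × 561 = 7.8). If the true incidence were double the expected value, the exact binomial chance of exceeding the limit would be:

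| Share of events captured | DVT/PE (0.8%, n = 1005) | AF (1.4%, n = 561) |
|---|---|---|
| 100% | 0.55 | 0.53 |
| 80% | 0.32 | 0.30 |
| 60% | 0.12 | 0.10 |

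**5. Size in 4.7.5.** If GP-recorded events are left out of the main analysis while all treatment weeks stay in, the fraction is d × (12 − w)/12. That is 0.5 × 6/12 = 25% to 0.9 × 10/12 = 75%, under the same assumption of no specialist capture.

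**6. Price of censoring.** The half-width grows roughly by 1/√(1 − U). At U = 5%, 0.39/√0.95 = 0.40% and 0.69/√0.95 = 0.71%. At U = 45%, 0.39/√0.55 = 0.53% and 0.69/√0.55 = 0.93%.

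**The case against.** - **GP-reported bleeds in the primary numerator.** A reader might infer that they too enter only a sensitivity analysis. The documents do not support this. Section 4.7.2 adjudicates on all SCEM questionnaires and follow-up, the GP form is one of those questionnaires, and 4.1 follows up outcomes known only to the GP. The sensitivity-only point belongs to 4.7.5 and 4.7.4.
- **Specialist capture after discharge.** A reader might also infer that nothing at all is seen after discharge. That goes too far. The specialist form is completed at least 12 weeks after the index date, and secondary-care charts may be accessed (3.0). Some major bleeds treated in hospital would plausibly be found. This reduces the bias but does not remove it.
- **Restriction in 4.7.5.** Incidence densities cover patients who continue rivaroxaban or whose stop date is known. If neither is known after discharge, this could be read as excluding that time. The text does not say so, and it sets no cut-off at discharge. A patient known to be on treatment would still contribute weeks without GP events.
- **Deferred handling.** Section 4.5.2 leaves the missing-data method to the steering committee at the interim stage, and no separate analysis plan is shown. Detail on missing forms could properly sit there. But the conflict between 4.1 and 4.7.2, the unadjusted proportion and the sensitivity label in 4.7.5 are in the protocol text itself. Section 4.5.2 describes missing variables in completed questionnaires and does not change the time-at-risk rule.
- **Mitigation.** Reminders to non-responders (4.4.3.1) and the acknowledgement of under-reporting (5.2) help, but neither changes the estimator.

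**Conclusion.** The point stands for 4.7.2 as a contradiction about when observation ends, combined with an estimator that treats unseen primary-care time as event-free. The direction is downward. For 4.7.5, and similarly 4.7.4, the weakness is that GP-recorded events are named only for a sensitivity analysis.

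A reader might take 5% to 45% as an estimate of the bias. It is not one: every input is assumed, and the formula supposes no specialist capture, so each figure is an upper value for its inputs. The protocol supports the mechanism through its expectation of shared care for most patients and of some GP non-response, but gives no number for either. The correction is still needed before analysis, because the primary denominator is ambiguous and one plain reading of it understates a major-bleeding risk.

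**What to change.** 1. Reconcile 4.1 and 4.7.2 on one rule: observed time ends at the earliest of event, stop + 2 days, day 84, death, or the discharge date when the GP form is missing or blank. Where a GP form with clinical content is returned, observation continues past discharge.
2. Make the figure compared with the trial range a 12-week cumulative incidence that allows for this censoring: Kaplan-Meier, which 4.7.2 already plans to plot, or an estimate with death as a competing event. Keep the simple proportion as a sensitivity analysis. Ending person-time at discharge without this step does not correct the proportion.
3. In 4.7.5 and 4.7.4, count confirmed GP-reported events in the main analysis and make the specialist-only count the sensitivity analysis. State whether treatment weeks after discharge count when no GP form is returned.
4. Compare patients discharged with and without a GP form, because the censoring is assumed to be non-informative.

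The cost is analysis wording and programming, plus the wider intervals shown above. The GP form's window already relies on the discharge date, but that date is not among the listed items in 4.4.2.3, so confirm that it is recorded.
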